8.2 SECONDARY EFFICACY OUTCOMES

• Number of reported menses within the 52-week follow-up period: We will use an identical approach compared to the primary outcome, namely a Poisson regression model via GLM and bootstrap Student's t test.

The following secondary efficacy outcomes will be compared between treatment groups using a mixed-effects regression modelling:

- Anthropometric measurements body composition, waist circumference, body weight
- Metabolic outcomes glycated plasma haemoglobin (HbA1c), plasma liver function tests, plasma lipid profile
- Arterial blood pressure
- Reproductive hormones serum luteinising hormone (LH), follicle-stimulating hormone (FSH), oestradiol, sex hormone binding globulin (SHBG), testosterone, free androgen index (FAI), dehydroepiandrosterone sulfate (DHEAS), androstenedione, Anti Mullerian hormone (AMH)
- Number of reported menses
- Glucose concentrations at the oral glucose tolerance test (OGTT)
- Hospital Anxiety and Depression Scale (HADS) score
- Multidimensional Health Profile: Health Functioning questionnaire score
- PCOS Health-Related Quality of Life score

- Modified Ferriam-Galwey hirsutism score
- Ludwig visual score
- Savin alopecia scale score
- Cardiff Acne Disability index
- Number of medications

We will fit mixed-effects linear models (random intercept models). In the fixed-effects parts of the models, we will include group (1 = obesity surgery, 0 = medical care) and time as a continuous outcome. We will use likelihood ratio tests to determine if there is an improvement in the model fit when including a treatment-by-time interaction, as evaluated using the Akaike information criterion. We will use a cutoff of a difference greater than 2 in AIC to indicate a significant improvement in the model.

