3.1 STUDY OUTCOME MEASURES

Primary outcomes

• Number of ovulatory cycles within the 12 month follow-up period. Ovulation will be defined as a rise in serum progesterone ≥16 nmol/L

Secondary outcomes

Change from baseline to 12 months. For each endpoint, temporal changes, mean levels and peak levels will be analysed as appropriate:

- Number of reported menses
- Body weight
- Waist circumference
- Body composition
- Plasma lipid concentration
- Plasma liver function tests
- Plasma HbA1c
- Arterial blood pressure
- Serum LH
- Serum FSH
- Serum Oestradiol
- Serum SHBG
- Serum Testosterone
- Serum free androgen index
- Serum DHEAS
- Serum Androstenedione
- Serum AMH
- Glucose concentrations at the OGTT
- Hospital Anxiety and Depression Scale score
- Multidimensional Health Profile: Health Functioning questionnaire score
- Social Functioning Questionnaire score

- PCOS Health-Related Quality of Life score
- Modified Ferriman-Galwey hirsutism score
- Ludwig visual score
- Savin Alopecia Scale score
- Cardiff Acne Disability Index
- Number of medications
- Adverse events
- pregnancy rates

Sub-studies

- Energy expenditure
- Sleep-disordered breathing
- Endometrial clonal activity
- Adipose tissue biology
- Brain responses to food

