2.2 FINAL ANALYSES AND REPORTING

2.2.1 FINAL ANALYSIS

Our study will involve collecting data from all participants for 52 weeks. Once this follow-up period is complete, the database will be locked, and no further modifications will be made to it. The final analysis of the primary and secondary outcomes, as outlined in the protocol and this statistical analysis plan (SAP), will only be performed using the locked database. In addition to presenting results at the main

time point of interest (52 weeks), findings will also be presented at the 26-week mark, along with the baseline measurements.

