3.2.2 SECONDARY EFFICACY ENDPOINTS

For each secondary endpoint, temporal changes, mean levels and peak levels will be analysed as appropriate:

- Anthropometric measurements body composition, waist circumference, body weight
- Metabolic outcomes glycated plasma haemoglobin (HbA1c), plasma liver function tests, plasma lipid profile
- Arterial blood pressure
- Reproductive hormones serum luteinising hormone (LH), follicle-stimulating hormone (FSH), oestradiol, sex hormone binding globulin (SHBG), testosterone, free androgen index (FAI), dehydroepiandrosterone sulfate (DHEAS), androstenedione, Anti Mullerian hormone (AMH)
- Number of reported menses
- Glucose concentrations at the oral glucose tolerance test (OGTT)
- Hospital Anxiety and Depression Scale (HADS) score
- Multidimensional Health Profile: Health Functioning questionnaire score
- PCOS Health-Related Quality of Life score
- Modified Ferriam-Galwey hirsutism score
- Ludwig visual score
- Savin alopecia scale score
- Cardiff Acne Disability index
- Number of medications

4 Sample Size

Based on the available data on the effect size of lifestyle interventions[1] and obesity surgery[2] on ovulation we estimated that women in the standard medical care group will have a mean of 7 and women in the obesity surgery group a mean of 10 ovulatory cycles in the 52-week follow-up period. With a standard deviation of 3.3 around both means, we will need 33 women in each group to have a 95% power to detect statistically significant differences between the groups at α of 0.05. We will recruit 40 patients in each group to account for a 15-20% drop-out rate based on rates in similar trials we have conducted in this field (LIPOS UTN: U1111-1126-3292 and DOMINO ISRCTN76278694).

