6 GENERAL ISSUES FOR STATISTICAL ANALYSIS

6.1 ANALYSIS SOFTWARE AND GENERAL METHODS OF ANALYSIS

We will use SPSS (version 27, IL, USA) for all analyses. Two-sided P-values < 0.05 will be considered statistically significant.

- *Primary outcome:* Number of ovulatory cycles
 - The primary outcome was considered a Poisson distributed variable. Thus, we will fit a generalised linear model (GLM) with the Poisson distributional family and a log link function.
- Secondary efficacy outcomes:
 - Continuous outcomes: We will fit mixed-effects linear models (random intercept models). In the fixed-effects parts of the models, we will include group (1 = obesity surgery, 0 = medical care) and time as a continuous outcome. Number of reported menses within the 52-week follow-up period: We will use an identical approach compared to the primary outcome, namely a Poisson regression model via GLM and bootstrap Student's t test.
- *Secondary safety outcomes:* Safety outcomes will be evaluated via Fisher's exact tests at 52 weeks.

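### For the secondary outcomes, SAP 8.2 lets an AIC rule choose between an all-visit average and a straight-line divergence, and defines no 26- or 52-week treatment contrast

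*SAP*

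**What the plan says.** SAP 8.2 (repeated in part in 6.1) fits linear mixed models with a random intercept to the secondary efficacy outcomes: anthropometry, metabolic and hormone measures, OGTT glucose, questionnaires, skin and hair scores, and medication count. For the fixed effects, "we will include group (1 = obesity surgery, 0 = medical care) and time as a continuous outcome". A treatment-by-time term is then tested for better fit: "We will use a cutoff of a difference greater than 2 in AIC to indicate a significant improvement in the model". The section names no categorical visit, curvature term, baseline covariate or stratification factor, and no contrast at a given week.

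Three other places bear on this:

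- SAP 2.2.1 makes week 52 the main time point and adds that "findings will also be presented at the 26-week mark, along with the baseline measurements".
- Protocol 3.1 heads the secondary outcomes "Change from baseline to 12 months".
- Protocol section 7 plans ANCOVA or chi-square comparisons adjusted for the stratification variables (BMI and site) and for the baseline value of the parameter.

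**The concern.** Without the interaction, the model has one group coefficient, which averages the arm difference over every modelled visit. With it, the arm difference is forced onto a straight line in time. These are different quantities, and the AIC rule picks one separately for each outcome. Two rows of the same results table could then answer different questions, and a repeat of the trial could switch a row from one to the other.

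Neither form is tied to week 52 or week 26. If the arms separate early and then stay apart, a straight line puts the effect in the wrong place. If the pre-treatment visit is among the outcomes, where randomisation makes the expected difference zero, the average is diluted and the line can show a baseline gap that does not exist. For exploratory outcomes the estimate and its interval are the result, so this matters even though no confirmatory claim rests on them.

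**Working it through.** **The plan's own figure.** The only design calculation is for the primary outcome: means of 7 and 10, SD 3.3, two-sided α 0.05, and "we will need 33 women in each group to have a 95% power". A noncentral t calculation gives power 0.947 at 32 per arm and 0.953 at 33, so that figure reproduces. The documents give no effect size, SD or power for the secondary models, so trajectories and correlations below are assumptions.

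**What the rule means.** The interaction adds one parameter, so the AIC gain is LR − 2. A gain above 2 means LR > 4 on 1 df, which is a pretest at p < 0.0455.

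**What the model estimates.** With balanced data and visit-specific arm differences d_j at times t_j:

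- without the interaction, the group coefficient is the mean of the d_j;
- with it, the fitted difference is a + bt, the least-squares line through the points (t_j, d_j).

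**Six-monthly outcomes, baseline as an outcome row.** Take t = 0, 26, 52 and d = 0, D, D.

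- No interaction: (0 + D + D)/3 = 0.67D.
- Slope: b = (−26·0 + 0·D + 26·D)/(26² + 26²) = 26D/1352 = D/52 per week.
- Baseline: 0.667D − 26·D/52 = 0.17D (true value 0).
- Week 26: 0.67D (33% too small).
- Week 52: 0.667D + 26·D/52 = 1.17D (17% too large).

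If the arms diverge linearly (0, 0.5D, D), the interaction model is exact, while the model without it gives 0.50D.

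**Six-monthly outcomes, follow-up visits only.** Two points determine a line, so the interaction model is exact. The model without it averages the two visits: D when both are D, and 0.90D when they are 0.8D and D.

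**Monthly outcomes.** Assume d(t) = (1 − e^(−t/τ))/(1 − e^(−12/τ)), with t in months, so the true 52-week difference is 1. With the interaction kept:

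| τ (months) | True wk 26 | Baseline modelled: wk 0 / 26 / 52 | Follow-up only: wk 26 / 52 |
|---|---|---|---|
| 2 | 0.95 | 0.43 / 0.81 / 1.18 | 0.85 / 1.11 |
| 3 | 0.88 | 0.32 / 0.75 / 1.17 | 0.78 / 1.12 |
| 4 | 0.82 | 0.25 / 0.70 / 1.15 | 0.73 / 1.11 |
| 6 | 0.73 | 0.17 / 0.64 / 1.12 | 0.66 / 1.09 |

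With baseline modelled, week 52 is 12–18% too large and week 26 is 12–15% too small. With follow-up visits only, the errors are 9–12% and 10–12%.

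**How often the rule keeps the interaction.** Simulation with 33 per arm, visits at 0/26/52 weeks, a plateau effect, and within-woman correlation 0.5–0.7 (assumed): 23–33% of trials at 0.3 SD, 50–72% at 0.5 SD, 88–98% at 0.8 SD and 100% at 1.5 SD.

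**Error rate.** The SAP does not say which term counts as a finding. Suppose either a retained interaction or a significant group effect does. In balanced data the first uses within-woman slopes and the second uses woman means, so they are independent under the null: 1 − (1 − 0.0455)(1 − 0.05) = 0.093. Simulation (correlation 0.5, 34 per arm, i.e. 40 × 0.85) gives about 0.10.

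**The case against.** Much of the other side's case stands.

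- **Baseline as an outcome row is not stated.** A reader might take it as fact, because a group-and-time model with no baseline covariate has no other way to express change from baseline. It remains an inference, and the 0.67D/0.17D/1.17D figures depend on it.
- **The plateau is assumed.** The protocol's rationale gives total weight loss and 12-month results, but no time course. Nothing in the documents supports one shape for hormones, mood scores and hair scores alike.
- **The documents allow several summaries.** Both list temporal changes, mean levels and peak levels, to be analysed as appropriate. An averaged difference and a slope difference roughly fit the first two. The SAP endpoint list no longer carries the protocol's change-from-baseline heading, and the 26-week findings could be descriptive. That permits different summaries, but it does not justify letting fit choose among them.
- **A plain loss of power does not follow.** One might set the group term alone against a week-52 ANCOVA and infer that the plan is underpowered. That comparison is mismatched, because the group-only model is not the one selected when the interaction is kept. At 0.6 SD (correlation 0.5, 34 per arm) the two-step procedure flags an effect in about 84% of trials. The cost is the error rate and the changing meaning of the estimate.
- **Large effects are not diluted.** At 1.5 SD the interaction was always kept. What remains is misplacement between weeks 26 and 52.

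**Conclusion.** The point holds on the SAP's explicit wording: linear time, an AIC rule that selects the reported effect, no 26- or 52-week contrast, and no adjustment for baseline or stratification variables despite protocol section 7. None of these depends on how baseline enters.

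The size does depend on it. With baseline modelled and a constant follow-up difference, errors are a 33% understatement at week 26 and either a 33% understatement (interaction dropped) or a 17% overstatement (interaction kept) at week 52. With follow-up visits only, six-monthly outcomes are exact if the interaction is kept, and monthly outcomes are off by roughly 10% on the assumed curves. There is no distortion if the arms truly diverge linearly and the interaction is kept.

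A reader might infer that the trial's main conclusion is at risk. It is not: the primary outcome has its own Poisson model, and SAP 6.5 labels all secondary outcomes exploratory. This should be fixed before database lock, but it is not critical to the trial.

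**What to change.** In SAP 8.2 and 6.1:

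1. Delete the likelihood-ratio/AIC selection step.
2. Enter visit as a categorical factor and always include treatment-by-visit.
3. State how baseline enters: as a covariate, or as an outcome constrained equal across arms.
4. Include BMI stratum and site, as protocol section 7 plans.
5. Name the covariance structure.
6. Report treatment contrasts with 95% confidence intervals at weeks 26 and 52, with week 52 as the main one.

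No new data are needed, and the model can be fitted with the mixed-model procedure in the planned SPSS. Six-monthly outcomes cost little. For monthly outcomes, 12 follow-up visits × 2 arms = 24 means replace four fixed effects (intercept, group, time, interaction), about 20 more parameters, so the covariance structure needs thought at this sample size. If that is too heavy, a week-52 ANCOVA on baseline and the stratification variables, with a matching week-26 analysis, would also give the contrasts.

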9 SAFETY ANALYSES

9.1 PRIMARY SAFETY OUTCOME

The primary safety outcome will be the incidence risk of treatment-emergent serious adverse events (SAEs) through the 52-week follow-up period. We will evaluate this outcome via a Fisher's exact test. Results will be presented as numbers of patients with the event (percentage).

9.2 Secondary Safety outcomes

We will use Fisher's exact tests to analyse all secondary safety outcomes (described in more detail below). The results will be reported numbers of patients with the event and percentages by treatment group.

9.3 Adverse Events

We will assess the number of participants with any treatment-emergent SAEs, any treatment-emergent adverse events (TEAEs), any-cause withdrawals/dropouts and the number of participants per severity grade. The Clavien-Dindo classification for grading the severity of complications will be used. Pregnancy rates will also be assessed and considered an adverse event.

9.3.1 ALL ADVERSE EVENTS

The total number of TEAEs and the number and percentage of subjects with at least one TEAE will be presented by treatment groups. A TEAE is an event starting or worsening in severity at or after initiation of the index procedure for the randomised treatment. For subject counts, subjects experiencing a given event more than once will be counted only once for that event.

A listing of all adverse events will include the subject number, adverse event (AE) number, the investigator description of the AE, the AE system organs class (SOC) and preferred term (PT), the severity of AE, whether or not the AE is classified as serious (SAE), the relationship of the AE to the procedure, the action taken, the outcome, and the adjudication status.

9.3.2 Adverse Events Leading to Withdrawal

A summary of number of TEAEs and of the incidence risk rates (number and percentage of subjects) of TEAEs leading to study withdrawal, by SOC and PT will be presented in a similar manner as

Imperial College

London

9.3.3 SERIOUS ADVERSE EVENTS

Summaries of serious TEAEs will be conducted in the same manner as for all TEAEs discussed above.

9.3.4 Deaths

If a death occurs during the trial, relevant information (including study day of death relative to index initiation, cause of death, and adverse event leading to death) will be supplied in a data listing.

10 OTHER PLANNED ANALYSES

10.1 PLANNED SUBGROUP ANALYSES

The planned subgroup analyses aim to explore the differential treatment effect of obesity surgery compared to medical care on the primary outcome:

- Baseline body mass index (BMI). This analysis will evaluate the treatment effect in patients with different baseline BMI values. Patients will be divided into two groups based on their baseline BMI, with one group having BMI <45 kg/m² and the other having BMI ≥45 kg/m².
- Baseline Homeostatic Model Assessment of Insulin Resistance (HOMA-IR) index. This analysis will evaluate the treatment effect in patients with different levels of insulin resistance. Patients will be divided into two groups based on their HOMA-IR value, with one group having HOMA-IR scores <4 and the other having HOMA-IR scores ≥4.
- 3. Baseline Free Androgen Index (FAI). This analysis will evaluate the treatment effect in patients with different androgen levels. Patients will be divided into two groups based on their FAI value, with one group having an FAI <7 and the other having an FAI ≥7.
- 4. Age at randomization. This analysis will evaluate the treatment effect on patients of different age groups. Patients will be divided into two groups based on age: one group aged <30 years and the other aged \geq 30 years.

For the above-mentioned analyses, we will use the same statistical methods described in section 8.

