5 ANALYSIS POPULATIONS

5.1 INTENTION TO TREAT POPULATION (ITT)

We will recruit 80 women, with each group comprising forty participants randomised at a 1:1 ratio. The intention-to-treat (ITT) population will include all patients who were initially assigned to either medical care or obesity surgery, regardless of any deviations from the trial protocol or the actual treatment they received. The analysis of this population will be based on their original assignment group.

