8 EFFICACY ANALYSES

8.1 PRIMARY OUTCOME

Number of ovulatory cycles

We will fit a GLM with the Poisson distributional family and a log link function. The Poisson model will be the primary analysis. Results will be presented as incidence rates and incidence rate ratios (95% confidence interval). Standard techniques will be employed to verify the model assumptions, which include residual analysis, overdispersion testing, and influence diagnostics. In case of substantial overdispersion, we may utilise a negative binomial model. As a sensitivity analysis, we will conduct a bootstrap t-test for independent samples. The analysis will include all participants who have complete follow-up data. We will use bias-corrected and accelerated (BCa) intervals via 10.000 replicates.

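### SAP 10.1 looks for effect modification by cutting BMI, HOMA-IR, FAI and age at single unexplained thresholds, with no treatment-by-modifier term; a continuous interaction would usually keep more information.

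*SAP*

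**What the plan says.** SAP 10.1 sets the aim: "The planned subgroup analyses aim to explore the differential treatment effect of obesity surgery compared to medical care on the primary outcome". It names four modifiers, all continuous, and divides each in two before analysis:

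- BMI, below 45 against 45 kg/m² or more ("Patients will be divided into two groups based on their baseline BMI").
- HOMA-IR, below 4 against 4 or more ("Patients will be divided into two groups based on their HOMA-IR value").
- FAI, below 7 against 7 or more ("Patients will be divided into two groups based on their FAI value").
- Age, below 30 against 30 years or more ("Patients will be divided into two groups based on age").

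The method is given in one sentence: "For the above-mentioned analyses, we will use the same statistical methods described in section 8". For the primary outcome that leads to SAP 8.1: "We will fit a GLM with the Poisson distributional family and a log link function". Section 8.1 contains no product of treatment with a baseline variable. The only interaction in section 8 is treatment-by-time, in 8.2, for the secondary outcomes.

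The size of the trial is fixed in SAP 5.1: "We will recruit 80 women, with each group comprising forty participants randomised at a 1:1 ratio". Neither document justifies the four cuts, states how many women are expected on each side, or gives power for any subgroup comparison.

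**The concern.** The question in 10.1 is about a gradient: does benefit rise or fall as BMI, insulin resistance, androgen level or age changes? A two-group split treats women just either side of the cut as different and all women on one side as alike. When the effect changes smoothly, this discards information, and more of it when the cut is off-centre. The loss comes from the cut, so a treatment-by-subgroup test would not recover it.

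The method is also incomplete. Without a treatment-by-modifier term, the section 8.1 model run in each subgroup yields two separate rate ratios and no estimate, confidence interval or test of the difference between them, which is what 10.1 sets out to explore.

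With at most 40 women per arm, there is little information on effect modification to begin with. What is at stake is the quality of these four exploratory analyses.

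**Working it through.** **Inputs from the plan.** Means 7 and 10 cycles, SD 3.3, 33 per arm needed and 40 recruited, drop-out 15–20% (SAP 4); 80 women, 1:1 (SAP 5.1); two-sided 0.05 (SAP 6.1).

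**Inputs not in the plan (assumptions).** A standard-normal modifier; a treatment effect that changes linearly by δ = 1.0, 1.5 or 2.0 cycles per SD of it; cuts at z = 0, 0.674 and 1.0, which give splits of 50/50, 75/25 and 84/16.

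**Step 1: the plan's own figure.** For a difference of 3 with SD 3.3, the two-sample t-test has power 0.947 at 32 per arm and 0.953 at 33. The stated 33 per arm is reproduced. Going from 40 to 33 is a loss of 7/40 = 17.5%, inside the stated drop-out range.

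**Step 2: information kept after a cut.** For a normal modifier and a linear interaction, cutting at quantile p leaves relative efficiency φ(z_p)² / [p(1 − p)], whatever the SD or δ.

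- 50/50: 0.3989² / 0.25 = 0.64, so 80 women act like about 51.
- 75/25: 0.54, so about 43.
- 84/16: 0.2420² / (0.8413 × 0.1587) = 0.44, so about 35. The smaller group would hold 0.16 × 40 ≈ 6 women per arm before drop-out.

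**Step 3: power by formula, one cell.** The standard error of the interaction per SD is 2 × 3.3/√N. At N = 80 this is 6.6/8.944 = 0.738. With δ = 1 the noncentrality is 1/0.738 = 1.355, giving power 27%. A median cut multiplies it by √0.637 = 0.798, to 1.081, giving 19%.

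**Step 4: power by simulation.** The model was y = 7 + 3g + δ·g·x + N(0, 3.3), where g is treatment and x the modifier, with 3,000 replicates per cell and a t-test of the interaction. Power in %:

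| Per arm | δ | Continuous | 50/50 | 75/25 | 84/16 |
|---|---|---|---|---|---|
| 40 | 1.0 | 26 | 18 | 16 | 13 |
| 40 | 1.5 | 50 | 33 | 28 | 22 |
| 40 | 2.0 | 74 | 54 | 45 | 36 |
| 33 | 1.0 | 22 | 16 | 14 | 12 |
| 33 | 1.5 | 42 | 28 | 25 | 20 |
| 33 | 2.0 | 65 | 46 | 40 | 30 |

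With δ = 0, rejection was 4.6–5.5% throughout. Repeat runs agree within about 3 points. At the median split the loss runs from 22 − 16 = 6 to 74 − 54 = 20 points. At 84/16 the largest loss is 74 − 36 = 38 here and 72 − 36 = 36 in a repeat, so about 37.

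**Step 5: the SAP's model family.** A Poisson log-link simulation at N = 80 (600 replicates), with log-rate interactions of 0.10 to 0.25 per SD, gave losses of 5 to 19 points at 50/50 and 9 to 27 at 80/20. Direction and order of size agree with Step 4.

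**Step 6: where the result weakens or reverses.**

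- True step of 3 cycles at the cut, 40 per arm: the split has about 52% against 35% for the continuous term (50/50), 39% against 23% (75/25) and 28% against 16% (84/16). The split wins.
- Lognormal modifier (log-SD 1, assumed), effect linear in its log at 1.5 cycles per SD, entered untransformed: 37% continuous against 35% split at the median. The advantage almost disappears.

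**The case against.** The strongest reply is that the size of the loss is not a property of this plan. The documents give no modifier distribution, split, interaction size or interaction shape. A reader might infer that the four analyses simply lose 6 to 38 points of power. They do not support that: the top of that range is one corner of an assumed grid (2 cycles per SD, 84/16), a median split costs at most about 20 points, and a true step at the cut favours the planned analysis. The entry criteria also truncate BMI at 35 kg/m² and age at 18 years, so a normal modifier is only an approximation. All of this stands, and the figures should be read as conditional.

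Second, the power quoted is for an interaction test that the SAP does not specify. That is true, but the absence of the term is part of the same gap and the same edit closes it.

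Third, the analyses are exploratory and the cuts are fixed in advance. A reader might infer that the thresholds were chosen from the data, or that the primary conclusion is at risk. Nothing in the documents supports either. Randomisation is stratified by BMI with no boundary stated; if 45 is that boundary, it would explain one cut of the four, and the SAP could say so.

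Fourth, a continuous term does not make these analyses well powered: at 1 cycle per SD it has about 22–26%. That stands too. It limits what the change can achieve but gives no reason to discard more information.

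**Conclusion.** The point holds in a conditional form. SAP 10.1 cuts four continuous modifiers at unexplained values, plans no continuous analysis, and relies on a model with no treatment-by-modifier term. If the effect varies linearly with a normal modifier, the cut keeps about 64% of the interaction information at a median split and about 44% at 84/16. With 33 to 40 women per arm and 1 to 2 cycles per SD, that is roughly 6 to 20 points of power at the median and up to about 37 at 84/16. The modifier distribution, split, interaction size and linear shape are all assumptions. The loss shrinks for a skewed modifier entered untransformed and reverses for a true step at the cut, although the SAP gives no reason to expect a step at any of the four values.

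This is a worthwhile improvement to exploratory analyses. The sample size and the primary result do not depend on it.

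**What to change.** In SAP 10.1, for each modifier in turn:

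- Add it to the section 8.1 model as a centred continuous covariate, together with its product with treatment. Use a log transformation where the variable is skewed, for example HOMA-IR and FAI.
- Report the ratio of rate ratios (per unit or per SD, on the scale used) with its 95% confidence interval, labelled exploratory.
- Check the functional form with a quadratic or spline term. The two-group results cannot do this, because two estimates do not separate a line from a step or a curve.
- Keep the results either side of 45, 4, 7 and 30 as descriptive displays only, and state where each cut comes from.

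The cost is SAP wording and one model per modifier, with no new data. The downside is that the model assumes a functional form, which a trial of this size can check only roughly, and that power for interactions remains limited, so the interval will say more than the p-value.

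### SAP 10.1 sets out to explore differential treatment effects but names no treatment-by-subgroup interaction, and the section 8.1 methods it relies on contain none

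*SAP*

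**What the plan says.** SAP 10.1 states the purpose: "The planned subgroup analyses aim to explore the differential treatment effect of obesity surgery compared to medical care on the primary outcome". It lists four baseline factors and cuts each into two groups: BMI at 45 kg/m², HOMA-IR at 4, free androgen index at 7 and age at 30 years. On method it says only "For the above-mentioned analyses, we will use the same statistical methods described in section 8".

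The part of section 8 that concerns the primary outcome is 8.1. It gives a Poisson GLM with log link (possibly negative binomial if overdispersion is substantial), reported as rates and rate ratios with 95% confidence intervals, and a two-sample bootstrap t-test as a sensitivity analysis. No subgroup variable or treatment-by-subgroup term appears there, elsewhere in the SAP, or in the protocol. Section 8.2 does contain an interaction, treatment by time, but only in the mixed models for secondary outcomes.

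SAP 6.1 sets the general threshold: "Two-sided P-values < 0.05 will be considered statistically significant". SAP 6.5 calls the secondary outcomes exploratory and leaves them unadjusted; it does not mention subgroups. No rule says how the two halves of a factor are to be compared.

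**The concern.** A differential effect is a difference between two treatment effects, so it needs an estimate of that difference with its own standard error. The 8.1 methods, applied in each half, give two treatment effects and no comparison between them. A two-sample t-test cannot carry an interaction term at all, so under 10.1 it can only be run half by half.

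Without the comparison, the easiest thing to notice is that one half is significant and the other is not. In a trial of 80 women that pattern is common even when every woman has the same expected benefit, because each half has much less power than the whole. At stake is what the trial appears to say about which women with PCOS gain from surgery.

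**Working it through.** **Inputs.** SAP section 4 assumes mean counts of 7 (medical care) and 10 (surgery). On sample size it states: "With a standard deviation of 3.3 around both means, we will need 33 women in each group to have a 95% power". Recruitment is 40 per arm (SAP 4 and 5.1), and alpha is 0.05 two-sided (SAP 6.1). The documents do not give the share of women in each subgroup. I assume 50:50 to 30:70, the same in both arms.

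**1. The plan's own figure.** n = 2(1.960 + 1.645)² × 3.3² / 3² = 31.5, so 32 per arm by the normal approximation. The noncentral t gives 33 (power 0.953 at 33, 0.947 at 32). Dropout: 33 / (1 − 0.175) = 40. The stated 33 and 40 reproduce.

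**2. One half significant and the other not, with an identical true effect.** With powers p₁ and p₂ in the two halves, the chance is p₁(1 − p₂) + p₂(1 − p₁).

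*t-test, 40 per arm.*
- 50:50 gives 20 per arm in each half, power 0.80 each: 2 × 0.80 × 0.20 = 0.32.
- 30:70 gives 12 and 28 per arm, powers 0.567 and 0.916: 0.567 × 0.084 + 0.916 × 0.433 = 0.44.
- With 33 per arm remaining, the same calculation gives 0.41 and 0.51.

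*Poisson model with its own standard error, true SD 3.3.* The log rate ratio is ln(10/7) = 0.357. For 20 per arm:
- Poisson SE = √(1/140 + 1/200) = 0.110.
- True SE = √(10.89/(20 × 49) + 10.89/(20 × 100)) = 0.129.
- Power = Φ((0.357 − 1.96 × 0.110)/0.129) = 0.86, so the chance is 2 × 0.86 × 0.14 = 0.24.
- For 30:70 the powers are 0.68 and 0.945, and the chance is 0.34.

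*Simulation* (gamma-Poisson counts, variance 10.89, 100,000 trials, 40 per arm):

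| Test | 50:50 | 30:70 |
|---|---|---|
| Poisson SE | 22% | 33% |
| Robust SE | 32% | 43% |

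**3. False-positive rate of an interaction test on the same data.** With robust standard errors the simulation gives 5.5% (50:50) and 5.7% (30:70). With Poisson standard errors, the SE is too small by the factor 0.110/0.129 = 0.856, so the rate is 2Φ(−1.96 × 0.856) = 0.093. The simulation also gives 9%.

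**4. Power of the interaction test for an interaction as large as the whole planned effect.** With a and b the per-arm sizes of the two halves, SE = 3.3√(2/a + 2/b).
- 50:50: SE = 1.476; Φ(3/1.476 − 1.96) = 0.53. The difference in effect detectable with 80% power is 2.80 × 1.476 = 4.1 cycles.
- 30:70: SE = 1.610; power 0.46; detectable difference 4.5 cycles.
- Log-rate scale with SD 3.3, ratio of rate ratios 1.43: power 0.50 and 0.44.
- With 33 per arm on the mean scale: 0.455 and 0.40.

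**5. Multiplicity.** Four interaction tests at 0.05 carry a family-wise error of 1 − 0.95⁴ = 18.5% if independent.

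**The case against.** The strongest defence is that 10.1 is under-specified and does not plan an invalid test. A reader might infer that the SAP intends to judge subgroups by separate p-values. The documents do not say so: 8.1 reports rate ratios with confidence intervals, no rule of interpretation is given, and a Poisson GLM can take a product term. Separate fits are the natural reading of cutting patients into two groups and pointing to 8.1, but that remains an inference.

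Other stronger readings also fail.
- Section 8 is not free of interaction terms, since 8.2 has treatment by time; the gap concerns treatment by subgroup.
- It is not established that the primary model is treatment-only, because 8.1 lists no covariates and protocol section 7 calls for adjustment for the stratification variables.
- The subgroups cannot all have 20 or fewer women per arm: if one half falls below 20, its partner exceeds it (12 and 28 at 30:70).
- A combined risk of a false contrast across all four factors would require these baseline factors to be independent, which nothing in the documents supports.

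The size also depends on the test. The higher range belongs to robust tests or the sensitivity t-test, while the planned Poisson standard error gives the lower one. If counts were truly Poisson, the closed form would give 18% to 31%.

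Finally, the SAP describes the aim as exploratory, the primary comparison is untouched, and an interaction test has little power here. All of that stands and limits the seriousness. It does not supply the missing comparison, and low power is a further reason not to contrast significance between halves.

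**Conclusion.** The point holds as a gap in specification: the stated aim is effect modification, and no stated method estimates or tests it. With an identical true effect, exactly one half of a factor would be significant in about 22% (50:50) to 32–33% (30:70) of trials with Poisson standard errors, and in about 32–44% with a robust test or t-test. A robust interaction test errs in 5–6%.

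These figures rest on the SAP's planning values, 40 women per arm with data, and assumed subgroup shares. Dropout or more uneven splits raise the discordance. The contrast becomes a false claim only if someone reads it as one; the SAP neither plans that reading nor guards against it. The point deserves correction before analysis, but it does not threaten the primary result.

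**What to change.** In SAP 10.1, for each factor, fit one model in all randomised women: the primary count model plus the subgroup variable and the treatment-by-subgroup interaction. Use standard errors that allow for overdispersion, since Poisson standard errors give about 9% false positives at SD 3.3. Report the ratio of rate ratios with its 95% CI and the interaction p-value. Show the subgroup rate ratios with CIs descriptively, and state that significance in one half and not the other will not be taken as evidence of a differential effect.

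State the limits as well: the four tests are exploratory and unadjusted, and power is roughly 50% or less for an interaction as large as the planned 3-cycle effect, so a null interaction will not show that effects are equal.

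The cost is one paragraph of SAP text. No new data are needed.
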